3. OBJECTIVES AND ENDPOINTS

Table 2: Trial Objectives and Endpoints

Objectives	Endpoint(s)
Primary	
To evaluate the effect of CK-3773274 on exercise capacity in patients with symptomatic oHCM	
 • Change in peak oxygen uptake (pVO₂) by cardiopulmonary exercise testing (CPET) from baseline to Week 24
Secondary	
To evaluate the effect of CK-3773274 on patient health status	
 • Change in Kansas City Cardiomyopathy Questionnaire – Clinical Summary Score (KCCQ-CSS) from baseline to Week 12 and Week 24
To evaluate the effect of CK-3773274 on New York Heart Association (NYHA) Functional Classification	
 • Proportion of patients with ≥1 class improvement in NYHA Functional Class from baseline to Week 12 and Week 24
To evaluate the effect of CK-3773274 on post-Valsalva left ventricular outflow tract gradients (LVOT-G)	
 • Change in post-Valsalva LVOT-G from baseline to Week 12 and Week 24 • Proportion of patients with post-Valsalva LVOT-G <30 mmHg at Week 12 and Week 24
To evaluate the effect of CK-3773274 on duration of eligibility for septal reduction therapy	
 • Duration of eligibility for septal reduction therapy (SRT) during the 24-week treatment period in patients who were eligible for SRT at baseline.
To evaluate the effect of CK-3773274 on exercise capacity	
 • Change in total workload during CPET from baseline to Week 24
Safety	
To evaluate the safety and tolerability profile of CK-3773274 in patients with symptomatic oHCM	
 • Incidence of reported major adverse cardiac events (cardiovascular [CV] death, cardiac arrest, non-fatal stroke, non-fatal myocardial infarction, CV hospitalization) • Incidence of new onset persistent atrial fibrillation • Incidence of appropriate implantable cardiac defibrillator (ICD) discharges and aborted sudden cardiac death • Incidence of left ventricular ejection fraction (LVEF) <50% • Incidence of LVEF <50% with at least one of the following: 
 ○ Signs and symptoms of heart failure (concomitant adverse event of heart failure or dyspnea), AND/OR ○ Increase in NT-proBNP (≥30% increase), relative to results from the most recent previous visit and above the upper limit of normal, at the time of LVEF assessment <50% • Incidence of treatment emergent adverse events

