8.4.1.3. Intensity of Adverse Events

The investigator must assess the intensity for each AE and SAE reported during the trial according to a three-point scale: mild, moderate, severe.

If the intensity of an AE worsens during IP administration, only the worst intensity should be reported on the AE page. If the AE lessens in intensity, no change in the severity is required.

The three categories of intensity are defined as follows:

Mild	The event is noticeable to the patient. It does not influence daily activities and does not require intervention.
Moderate	The event makes the patient uncomfortable. Performance of daily activities are influenced, and intervention is needed.

Severe	The event causes noticeable discomfort and interferes with daily activities. The patient may not be able to continue in the trial, and treatment or intervention is needed.
---------------	---

A mild, moderate, or severe AE may or may not be serious. Medical judgment should be used on a case-by-case basis.

Seriousness, rather than severity assessment, determines the regulatory reporting obligations.

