9.4.5.1. Adverse Events

A treatment-emergent AE is an AE with an onset after initiation of IP, or an AE present at initiation of IP dosing that worsens in severity during the treatment. AEs will be coded using MedDRA dictionary and summarized by preferred terms and system organ class. The version of the MedDRA dictionary will be specified in the clinical study report. AEs will be classified according to severity. The number and percentage of patients reporting AEs will be tabulated.

Only treatment-emergent AEs with an onset from the first dose until 4 weeks after last dose of IP will be summarized. All AEs will be included in patient listings.

Patient incidence of reported major adverse cardiac events (CV death, cardiac arrest, non-fatal stroke, non-fatal myocardial infarction, CV hospitalization) will be summarized by treatment group and event type. Patient incidence of new onset persistent atrial fibrillation, patient incidence of appropriate ICD discharges and aborted sudden cardiac death, patient incidence of LVEF <50% will be summarized by treatment group.

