2.2.4. Safety Endpoints

- Incidence of reported major adverse cardiac events (cardiovascular [CV] death, cardiac arrest, non-fatal stroke, non-fatal myocardial infarction, CV hospitalization)
- Incidence of new onset persistent atrial fibrillation
- Incidence of appropriate implantable cardiac defibrillator (ICD) discharges and aborted sudden cardiac death
- Incidence of LVEF <50% with at least one of the following:
 - Signs and symptoms of heart failure (concomitant adverse event of heart failure or dyspnea)AND/OR
 - Increase in NT-proBNP ($\geq 30\%$ increase), relative to results from the most recent previous visit and above the upper limit of normal, at the time of LVEF assessment <50%

Note signs and symptoms refer to AEs with onset date within ± 7 days relative to the date when LVEF $<50\%$.

- Incidence of LVEF $<40\%$
- Incidence of LVEF $<50\%$

Incidence of LVEF below 40% and 50% will be summarized for site read, core lab read and both.

- Incidence of treatment emergent adverse events (TEAEs)

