5.7.8. Other Study Related Definitions

Actual Dose Group

Patients in the aficamten actual treatment group will be identified as 5 mg, 10 mg, 15 mg, 20mg or discontinuing IP prior to dose adjustment based on the dose assigned at Week 8. If a patient discontinues IP prior to the start of Week 8 (IWRS Week 8 dispensation), then the subject will be

identified as discontinued IP prior to achieve stable dose. The actual dose group may be used in selected displays.

Investigational Product Exposure Period

For subjects dosed with IP:

$[(\text{Last IP administration date} - \text{date of Study Day 1}) + 1]/7$ (in weeks)

Interruptions recorded in the eCRF page will be excluded from the expected dose calculation.

Treatment-emergent Adverse Event

For the purpose of reporting, an investigator-reported event starting on or after first dose of IP and up to and including 28 days after the last dose date of IP will be labeled as a treatment-emergent AE.

Last Titrated Dose

Last titrated dose is defined as the last titrated dose assigned to the patient during the 24 Week treatment period.

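### The SAP labels treatment-emergent AEs by onset date only and drops, without comment, the protocol's limb for AEs that worsen on treatment

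*SAP*

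**What the plan says.** Protocol section 9.4.5.1 gives a definition with two limbs. The first is onset: "A treatment-emergent AE is an AE with an onset after initiation of IP". The second is worsening: "or an AE present at initiation of IP dosing that worsens in severity during the treatment". Its next paragraph then restricts the tables: "Only treatment-emergent AEs with an onset from the first dose until 4 weeks after last dose of IP will be summarized".

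SAP section 5.7.8 introduces its rule as one for reporting and labels as treatment-emergent "an investigator-reported event starting on or after first dose of IP", with an upper limit of 28 days after last dose. There is no worsening limb. SAP sections 8, 8.1, 8.2.1 and 8.2.2 do not restore it, and the SAP version history does not mention the change.

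Both documents list the endpoint: "Incidence of treatment emergent adverse events" in Protocol section 3, and the same item in SAP section 2.2.4.

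Three protocol rules govern how such events reach the database:
- Section 8.4.1.6: between consent and first dose only procedure-related events are entered as AEs; other occurrences go to medical history.
- Section 8.4.1.1: an exacerbation of a pre-existing condition is itself an AE.
- Section 8.4.1.3: when an AE becomes more intense during IP administration, "only the worst intensity should be reported on the AE page".

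**The concern.** One named safety endpoint has two definitions, and the one that will be programmed is the narrower. Protocol section 9.4 gives the SAP the task of adding technical detail, and SAP section 1 describes itself in the same way; neither suggests that the SAP may redefine an endpoint. Nor does the SAP look like the later word. It took effect on 09 October 2023, and Protocol Amendment 04, dated 08 December 2023, still carries the worsening limb.

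The second limb is there to catch deterioration on drug of something that began before it. If that limb is absent from the TEAE flag, such an event drops out of every summary built on the flag, including the serious, severe, drug-related and discontinuation tables in SAP sections 8.1 and 8.2.1. Taken alone, the missing limb can only remove events.

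**Working it through.** There is no plan figure to reproduce. The check compares the rules on test cases and then asks which patients fall into the gap.

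**1. Windows.** The protocol uses 4 weeks after last dose and the SAP 28 days: 4 × 7 = 28. They agree, so the worsening limb is the substantive difference.

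**2. Three cases under each rule.**

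| Case | Protocol definition | Protocol summary sentence, read literally | SAP 5.7.8 |
|---|---|---|---|
| New onset on IP | TEAE | In tables | TEAE |
| Pre-dose AE that worsens on IP | TEAE | Not in tables | Not a TEAE |
| Pre-dose AE that does not worsen | Not a TEAE | Not in tables | Not a TEAE |

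Only the second row differs. There the SAP departs from the protocol's definition but matches a literal reading of the protocol's own summary sentence.

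**3. Who is in the second row.** A condition held in medical history that flares on treatment is an AE under Protocol 8.4.1.1. Entered with its on-treatment start date, it meets the SAP rule and is not lost. What remains is an AE already on the AE page before first dose. By Protocol 8.4.1.6 that means a procedure-related event, and it must still be present at dosing and then worsen.

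**4. What date such an event carries.** Protocol 8.4.1.3 asks for the worst intensity. It does not ask for a new record or a new onset date, and it does not discuss AEs opened before IP. The likely result is one record with its pre-dose start, which the SAP rule excludes. This is an inference from the text.

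**5. Size.** The documents give no rate. For scale only, let p be the proportion of patients with such a screening event and q the fraction of those events that worsen. The number affected is 270 × p × q. With assumed p = 1% to 3% and q = 1/3:
- low: 270 × 0.01 × 1/3 = 0.9
- high: 270 × 0.03 × 1/3 = 2.7

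Both rates are assumptions with no support in the documents. The result shows only that the order of magnitude is a handful at most under such rates.

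**The case against.** The strongest reply is that the SAP follows the protocol's tabulation rule. A reader might infer that the SAP strips from the tables events that the protocol requires there. The documents do not support that: the summary sentence in Protocol 9.4.5.1, taken literally, excludes the same events. This part of the objection stands, so the conflict over tables is arguable. It does not remove the conflict over the definition. It also leaves the protocol with a worsening limb that would never affect a summary, and the SAP does not say that it has chosen between the two sentences.

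A reader might also infer that Protocol 8.4.1.3 instructs sites to keep the pre-dose onset date. It does not say so. CRF completion instructions, which are not among the documents, could direct otherwise.

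A third tempting inference is that TEAE incidence overall is biased downward. That holds only for the missing limb. SAP section 5.8.3 sets a wholly missing onset to the first dose date, and does the same when only the day is missing and month and year match first dosing. Those rules push uncertain events into TEAE status.

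Finally, the consequences are limited. Safety analyses are descriptive and all AEs are listed whatever their flag. Major adverse cardiac events, atrial fibrillation, ICD discharges and LVEF thresholds are separate endpoints. The heart-failure qualifier for LVEF below 50% uses AE onset within 7 days either side of the LVEF date, not TEAE status. All of this stands and is why the point is minor.

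**Conclusion.** Wrong as written, but minor. It is certain that SAP 5.7.8 does not carry the protocol's definition of a listed safety endpoint and gives no reason. It is arguable whether the tables would differ from what the protocol intends, because the protocol is in tension with itself and the SAP resolves it silently against the worsening limb. It is probable, not stated, that a procedure-related AE opened before first dose that worsens on IP would be missed by the TEAE tables; it would still appear in listings. The number of such events is unknown, and the 0.9 to 2.7 of 270 patients shown above rests wholly on assumed rates. No efficacy result or error rate is affected.

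**What to change.** 1. **SAP 5.7.8:** add the second limb, so that an AE already there when IP starts also counts if its severity increases during treatment. Keep it to the treatment period, as the protocol does; the 28-day extension belongs to the onset limb.
2. **Protocol 9.4.5.1:** reword the summary sentence so that it refers to onset or worsening, which makes it consistent with the definition before it.
3. **Data rule:** identify worsening from a recorded date of worsening or from a recorded pre-dose severity. A date is preferable, because SAP 8.1 tabulates AEs by dose level at onset and a pre-dose onset has none.
4. **Protocol 8.4.1.3:** clarify how the worst-intensity rule applies to AEs opened before first dose. Simply asking for a new AE entry would sit badly with the present text.

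If onset-only is what the sponsor wants, the alternative is to say so, justify it, and remove the worsening limb from the protocol definition.

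The cost is one SAP clause, one reworded protocol sentence and one data-entry clarification. The downside is a slightly higher TEAE count.

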5.7.9. Derived Echocardiographic Parameters

The following BSA-indexed variables will be derived using the baseline BSA defined in [Section 5.7.2](#):

- $\text{LVEDV-I (mL/m}^2\text{)} = \text{LVEDV/BSA}$
- $\text{LVESV-I (mL/m}^2\text{)} = \text{LVESV/BSA}$
- $\text{LVSVI (mL/m}^2\text{)} = \text{LVSV/BSA}$
- $\text{LAV-I (mL/m}^2\text{)} = \text{LAV/BSA}$
- $\text{LVCO-I (mL/min/m}^2\text{)} = \text{LVCO/BSA}$
- $\text{LVmass-I(g/m}^2\text{)} = \text{LVmas/BSA}$

For the presentation of results, the BSA-indexed variables will be rounded to the same number of decimal places as the corresponding non-indexed variables provided by the echocardiography core laboratory.

5.8. Handling of Missing Data

5.8.1. Missing Efficacy Endpoints

For the primary endpoint, missing data will be imputed under missing at random (MAR) assumption and all observed and imputed missing pVO₂ assessments will be included in the primary analysis of the primary endpoint. Missing secondary CPET endpoints will be handled the same as for the primary endpoint. Missing response for patient reported outcomes will be handled as described in [Section 11.1](#).

5.8.2. Missing Start and Stop Dates for Prior and Concomitant Medication

To classify medications as baseline use or concomitant, missing start and stop dates of medications will be imputed as follows:

- If the medication start date day is missing, it will be imputed with the first of the month,
- If the medication start date day and month are missing, they will be imputed with 01 January,
- If the medication stop date day is missing, it will be imputed with the last day of the month or the date of the last contact with the patient, with the imputed date doesn't exceed the date of last contact,
- If the medication stop date day and month are missing, they will be imputed with 31 December or the date of the last contact with the patient, with the imputed date doesn't exceed the date of last contact,
- For the ongoing medications, the stop date will not be imputed.

5.8.3. Missing Start and Stop Dates for Adverse Events

For AEs with incomplete date information recorded in the eCRF, the imputation will follow the following algorithm:

For missing AE onset Date

- If an AE onset Day is missing and the Month of AE onset is known, then the first day of the month of AE onset will be imputed as the AE onset date. If the month and year of AE onset are the same as month and year of the first dosing, the missing day will be imputed as the first dosing date.
- If AE onset information is not available, then the first dosing date will be imputed as the AE onset date.
- If AE onset day and month are both missing, the missing month and day will be imputed as 01 January. If the year of AE onset is the same as the first dosing date, the AE onset will be imputed as the first dosing date.

For missing AE end Date:

- If the AE end Day is missing and it will be imputed with the last day of the month or the date of the last contact with the patient, with the imputed date doesn't exceed the date of last contact.
- If the AE end date day and month are missing, they will be imputed with 31 December or the date of the last contact with the patient, with the imputed date doesn't exceed the date of last contact.
- For the ongoing AEs, the stop date will not be imputed.

6. STUDY POPULATION

6.1. Subjects Disposition

Patient disposition will be summarized based on all randomized patients. The following will be summarized:

- The number and percentage of patients who completed the study and the number of patients who discontinued from the study early,
- For the patients who discontinued from the study early, reasons for early discontinuation,
- The number and percentage of patients who received at least one dose of the IP,
- For the patients who received at least one dose of the IP, the number and percentage of patients who completed study treatment and the number of patients who discontinued the study treatment early,
- For the patients who discontinued the study treatment early, reasons for early discontinuation.

The number and percentage of randomized patients included in each analysis set will be summarized. Reasons for exclusion from analysis sets will be listed.

6.2. Screen Failures

Screen failures will be listed and summarized by reasons of screening failure.

6.3. Protocol Deviations

Major protocol deviations are reviewed and confirmed by the protocol deviation classification committee (PDCC) during the protocol deviation reviews throughout the study prior to database lock. Major protocol deviations are a subset of protocol deviations that may significantly impact the completeness, accuracy, and/or reliability of the study data or that may significantly affect a subject's rights, safety, or well-being. E.g., of major protocol deviations are

- patients who entered the study even though they did not satisfy the entry criteria.
- patients who developed withdrawal criteria during the study but were not withdrawn.
- patients who received the wrong treatment or incorrect dose.
- patients who received an excluded concomitant treatment.

Number of patients with reported major protocol deviation will be summarized by treatment group for all randomized subjects. A summary of protocol deviations due to COVID-19 will be provided separately.

6.4. Demographic and Baseline Characteristics

Demographic and baseline characteristics, including age, age group [< 65 , ≥ 65], sex, race, ethnicity, height, weight, BMI, BSA, randomization stratification variables and baseline disease characteristics will be summarized by randomized treatment group for the FAS using descriptive

statistics. Summary may be repeated for all randomized patients. All randomized patients will be included in the listing of demographic and baseline characteristics.

6.5. Listing of Subject Inclusion and Exclusion Criteria

A listing of randomized patients who did not meet the inclusion and exclusion criteria will be provided.

6.6. Medical History

Medical history will be summarized by treatment received for the Full Analysis Set. HCM-related medical history will be summarized, including time since initial diagnosis and number and percentage of patients meeting the oHCM criteria.

Select cardiovascular medical history and other medical history will be summarized by the Medical Dictionary for Regulatory Activities Terminology (MedDRA) system organ class (SOC) and preferred term (PT).

6.7. Baseline Medications Use

Medications will be coded using World Health Organization (WHO) Drug Dictionary. Baseline medication use is defined as medications that start before the first dose of IP and ends after the first dose of IP or ongoing. The count and percentage of patients with each medication history item will be presented by therapeutic class (Anatomical Therapeutic Chemical [ATC] Class 3) and preferred name. If ATC Class 3 is not available, ATC Class 2 will be used in the summary.

7. EFFICACY

7.1. General Considerations

Efficacy analyses will be performed in the FAS by the randomized treatment group. Unless otherwise specified, all hypothesis tests will be reported as 2-sided p-values. Exploratory endpoints and subgroup analyses will be assessed using a nominal alpha level of 0.05 and will not have multiplicity adjustments. In order to preserve an overall type I error rate for the primary and secondary endpoints testing of the primary and secondary endpoints will follow the testing procedures specified in [Section 7.6](#).

7.2. Testing Statistical Assumptions Including Comparability at Baseline

The primary endpoint will be analyzed using an analysis of covariance (ANCOVA) model. Model assumption will be assessed by graphical examination of residuals. If assumptions are substantially violated, rank based analysis will be performed as supportive analysis. See [Section 7.7.4](#) for more details.

7.3. Statement of the Null and Alternate Hypotheses

The null hypothesis for the primary endpoint is that the treatment difference (aficamten – placebo) of mean change from baseline of pVO₂ at Week 24 is 0 and the alternative hypothesis is that the treatment difference is > 0 (favors aficamten). The tests will be reported with two-sided p-values, but only the direction favoring aficamten direction will be considered success.

7.4. Planned Covariates

Baseline covariates include but are not limited to the stratification factors and baseline measurements. For CPET related endpoints, covariates age, sex, baseline weight will also be evaluated. See [Section 7.7.4](#) for details evaluating covariates effect in the primary endpoint.

7.5. Subgroup Analyses

Subgroup analyses with relatively moderate sample size will be performed to examine the consistency of the observed treatment effect and to gain insight into the effectiveness of aficamten in subpopulations. Analyses of the primary endpoint will be conducted for the following subgroups:

- Sex (male, female)
- Age group (< 65, ≥ 65 years old)
- Baseline body mass index (<30 vs. ≥ 30)
- Baseline NYHA Class (II, III)
- Baseline KCCQ CSS (≤ median and > median)
- Baseline LVEF (≤ median and > median)
- Baseline N-terminal prohormone brain natriuretic (NT-proBNP) (≤ median and > median)

- CPET modality (treadmill, bicycle)
- Baseline pVO₂ (\leq median, $>$ median)
- Beta Blocker (use, no use)
- Baseline resting LVOT (\leq median and $>$ median)
- Sarcomeric gene mutation status (pathogenic or variant of uncertain significance, and non-disease causing or none)

Subgroup analysis will be performed by including the subgroup effect and subgroup by treatment interaction to the model. The subgroup analysis will be performed based on the imputed dataset generated for the primary analysis of the endpoint if the primary analysis is based on multiple imputation.

In addition, subgroup of IND site status (IND sites vs. non-IND sites) analysis will be performed for the primary estimand, proportion of patients with >1 NYHA functional class improvement, KCCQ CSS change from baseline, post-Valsalva LVOT-G change from baseline at Week 24 and overall adverse events summary to demonstrate compliance with relevant aspects of 21 CFR 312.120.

Analyses on the primary and secondary endpoints in patients who were SRT eligible at baseline may be explored.

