3.3. Sample Size Considerations

3.3.1. Sample Size Justifications

Assuming a difference in change from baseline in pVO₂ of 1.5 mL/kg/min for CK-3773274 compared to placebo, a standard deviation (SD) of 3.5 mL/kg/min, accounting for limiting beta-blocker use (less than ~70%), limiting exercise modality of bicycle (less than ~50%) and 10% of patients missing change from baseline data of the primary endpoint, a sample size of 270 patients at randomization ratio of 1:1 (approximately 135 randomized to CK-3773274 and 135 randomized to placebo) provides more than 90% power to detect the difference in pVO₂ change from baseline to Week 24 with a 2-sided type I error of 0.05.

During the study, Cytokinetics will periodically assess in a blinded fashion the aggregate pooled missing data rate and overall pooled SD for the change from baseline in pVO₂ at Week 24. If the pooled SD is larger than expected, Cytokinetics may consider increasing the sample size once in order to maintain the intended power.

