The imputation model will use regression multiple imputation which includes treatment group, randomization stratification factors, baseline pVO₂, sex, age, baseline hemoglobin, baseline body weight, baseline KCCQ CSS, and baseline NYHA class and the last available post randomization NYHA functional class, resting and Valsalva LVOT. Categorical variables, i.e., treatment group, baseline NYHA functional class, and sex will be specified in the CLASS statement. One hundred

(100) imputed datasets will be generated. Change from baseline in pVO₂ will be calculated based on the observed and imputed data. Each of the imputed dataset will be analyzed using the primary analysis ANCOVA model. LSM estimate of treatment difference and the standard error will be combined using Rubin's rules ([Rubin 1987](#)) to produce a LSM estimate of the treatment difference, its 95% confidence interval, and p-value for the test of null hypothesis of no treatment effect. LSM, LSM difference and the corresponding standard error, 95% CI and p-value will be presented.

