7.7.3. Subgroup Analyses for the Primary Endpoint

Subgroup analyses will be performed by including the subgroup effect and subgroup by treatment interaction terms to the primary ANCOVA model for the primary endpoint. For subgroup analysis for the primary estimand, missing data imputed in the primary analysis will be used in the subgroup analyses. Only summary statistics will be presented for the subgroup level when the number of subjects in either treatment arm is ≤ 15 at this level. LSM estimate of the treatment difference, 95% confidence intervals for the mean treatment difference and nominal p-values will be provided for each subgroup level.

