7.7.4. Supportive Analyses for the Primary Endpoint

To explain heterogeneity or identify treatment effect modifiers from the baseline characteristics, covariates used to define pre-specified subgroups and these covariates by treatment interaction

terms will be included in the ANCOVA model as supportive analysis. Global test of covariates by treatment interactions will be performed.

Stepwise model selection method will be used based on the stay or entry level of 0.05 to evaluate significant baseline covariates impact on the primary endpoint. ANCOVA model will be repeated by adjusting for the significant baseline covariates. Covariates measured as continuous will be introduced to the model as continuous variable. These analyses will be based on observed data.

The normality assumptions of the ANCOVA model will be investigated graphically. The scaled residuals will be examined. A supportive analysis will be performed after transforming pVO₂ data into ranks if greater than 5% of patients have an extreme change from baseline value at Week 24. Extreme values in the pooled data are defined as observations outside of Tukey's outer fences, i.e. observations that are less than the 25% quartile – 3 times the inter quartile range or greater than 75% quartile + 3 times the inter quartile range. Ranks will be applied to all changes from baseline data after the imputation step. Baseline data will be ranked separately.

The secondary estimand will be analyzed using the same primary analysis ANCOVA model for the primary estimand. Subgroup analysis for the secondary estimand will be performed using the same ANCOVA model for the subgroup analysis for the primary estimand.

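### Subgroup effects on pVO2 are estimated from imputations with no treatment-by-subgroup terms, so a true subgroup difference is pulled toward zero by up to the missing fraction (under 10%)

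*SAP*

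**What the plan says.** SAP 7.5 sets out twelve subgroup factors for the primary endpoint, to be analysed by adding subgroup and subgroup-by-treatment terms to the model. On missing data it says: "The subgroup analysis will be performed based on the imputed dataset generated for the primary analysis of the endpoint", provided that analysis uses multiple imputation. SAP 7.7.3 repeats this for the primary estimand: "missing data imputed in the primary analysis will be used in the subgroup analyses".

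The imputation model is in SAP 7.7.1: "The imputation model will use regression multiple imputation which includes treatment group, randomization stratification factors". The list continues with baseline pVO2, sex, age, hemoglobin, weight, KCCQ-CSS and NYHA class, and the last post-randomization NYHA class and resting and Valsalva gradients. No product terms are named, and the sample code in SAP 11.5 specifies none.

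Two other provisions bear on the point:

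- SAP 7.7.2 replaces MAR imputation with placebo-based imputation in the primary analysis if 10% or more of the data are missing, or if 5% or more of patients have data missing for reasons related to study drug.
- SAP 7.7.4 plans subgroup analyses of the secondary estimand, which Table 5 restricts to patients who completed treatment and have an observed Week 24 pVO2.

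**The concern.** The analysis model contains an interaction that the imputation model lacks. Observed patients carry whatever subgroup difference exists. Imputed patients carry almost none, except what reaches them through their last NYHA class and gradients. Pooling the two dilutes the interaction.

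The stated purpose of these analyses is to check that the treatment effect is consistent across subgroups, and this method leans toward finding it so. What is at stake is the description of subgroup effects. The analyses are nominal and outside the multiplicity procedure (SAP 7.1), and the overall treatment effect is not in question.

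**Working it through.** **Inputs from SAP 3.3.1.** Planned effect: "Assuming a difference in change from baseline in pVO₂ of 1.5 mL/kg/min for CK-3773274 compared to placebo". Spread: "a standard deviation (SD) of 3.5 mL/kg/min". Missingness: "10% of patients missing change from baseline data of the primary endpoint". Size: "a sample size of 270 patients at randomization ratio of 1:1".

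**Assumptions, not in the documents.** A true subgroup difference of 2.0 mL/kg/min, a 50/50 subgroup split, and data missing completely at random unless stated otherwise.

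**The plan's own figure.** With 10% missing, n per arm = 135 × 0.9 = 121.5. SE = 3.5 × √(2/121.5) = 0.449, and 1.5/0.449 = 3.34. Power = Φ(3.34 − 1.96) = 91.6%, which agrees with the stated figure of more than 90%.

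**Expected shrinkage.** Let m be the missing fraction and δ the true difference. If no interaction reaches the imputed patients, the expected estimate is about (1 − m)δ + m × 0:

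- m = 0.05: 0.95 × 2.0 = 1.90
- m = 0.09: 0.91 × 2.0 = 1.82
- m = 0.10: 0.90 × 2.0 = 1.80

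SAP 7.7.3 reports effects per subgroup level. With a 50/50 split each level moves by half the shift, or 0.05 at m = 0.05.

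**Standard error of the interaction.** For four equal cells it is 4 × 3.5/√N(observed). At 5% missing, 14/√256.5 = 0.874. At 10% missing, 14/√243 = 0.898.

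**Simulation.** 1,500 trials per setting, N = 270 allocated 1:1, residual SD 3.5, 100 regression imputations, Rubin's rules, true difference 2.0, no post-randomization auxiliary:

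| Missing | Data used | Mean estimate | Reported SE | Actual SD | RMSE | Power |
|---|---|---|---|---|---|---|
| 5% | Imputed, no interaction (as in SAP) | 1.91 | 0.880 | 0.850 | 0.854 | 60% |
| 5% | Imputed, with interaction | 2.02 | 0.880 | 0.897 | 0.897 | 63% |
| 5% | Observed only | 2.02 | 0.879 | 0.896 | 0.896 | 63% |
| 10% | Imputed, no interaction (as in SAP) | 1.80 | 0.902 | 0.812 | 0.835 | 53% |
| 10% | Imputed, with interaction | 2.00 | 0.904 | 0.902 | 0.902 | 60% |
| 10% | Observed only | 2.00 | 0.903 | 0.901 | 0.901 | 60% |

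The 10% rows sit exactly at the SAP 7.7.2 trigger, so they bound the MAR case rather than fall inside it. A separate simulation gave 1.88 at 5% missing and 1.81 at 9%, with power at 9% falling from 60% to 53%.

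**Variations at 10% missing:**

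- Subgroup main effect left out of the imputation model: ratio to truth 0.90, the same as with it included.
- Subgroup prevalence 30%: ratio 0.90.
- No true interaction: mean estimate 0.00, rejection rate 4.2%.
- A post-randomization auxiliary correlated 0.5 with pVO2: ratio 0.90 if none of the interaction passes through it, 0.96 if half does, and 1.01 (no shrinkage) if all does.

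**Precision.** At 10% missing, mean/SD is 1.802/0.812 = 2.22 with the SAP imputations and 2.005/0.901 = 2.23 with observed data. The smaller spread is therefore shrinkage and brings no extra information. Rubin's SE does not show it, so intervals are slightly wide (coverage 96% against 95%).

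**The case against.** The strongest reply is that the effect is small and may vanish. The MAR model applies only below 10% missing, and SAP 7.7.1 expects few missing tests. At 5% missing the shift is about 0.1 against an SE of 0.88, roughly one-ninth of a standard error. The assumed difference of 2.0 exceeds the whole planned effect of 1.5; at a difference of 1.0 with 5% missing, the estimate is 0.95 rather than 1.00. Protocol 4.2 expects exercise benefit to follow gradient reduction, and the last gradients are in the imputation model, so much of a real interaction could be preserved. All of this stands. It limits the size but does not remove the mechanism.

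The case against also corrects four stronger readings:

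- **Attenuation of 10% or more.** A reader might extend the arithmetic to higher missing rates, or to 5% missing in one half and 20% in the other (12.5% overall). SAP 7.7.2 would by then have replaced the MAR imputation. Placebo-based imputation forms its input datasets differently (SAP 11.5), and its effect on subgroup estimates was not quantified here.
- **A less accurate estimator.** Only the reported SE fails to improve. The actual spread and RMSE are somewhat smaller with the SAP imputations.
- **Two interaction analyses on different data.** SAP 7.7.4 says "These analyses will be based on observed data", but the sentence closes the paragraph on stepwise selection. It may not govern the global interaction test in the paragraph before, so the text does not establish a conflict.
- **Observed data as a free substitute.** An observed-data analysis drops the NYHA and gradient information that supports MAR. When missingness depended on the gradient auxiliary and the whole interaction passed through it, observed data gave 1.91 and 1.95 in two sets of runs. SAP 7.7.4 already supplies an observed-completer view through the secondary estimand.

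**Conclusion.** The point holds as a minor one. Under the MAR primary analysis, any true subgroup difference in pVO2 is pulled toward zero by up to about the missing fraction. That is under 10%, and less or none to the extent that post-randomization NYHA class and gradients carry the interaction. For an assumed difference of 2.0 mL/kg/min and an SE near 0.9, the shift is about 0.1 at 5% missing and under 0.2 throughout. Power for the interaction falls by about 3 points at 5% missing and 7 points at 9%.

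The size rests on the assumed difference; the shrinkage ratios rest on data missing completely at random and on the assumed share carried by the auxiliaries. The cause is the absence of treatment-by-subgroup terms. Omitting BMI, LVEF and the other main effects did not change the size.

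A reader might infer that the plan manufactures consistency or compromises the primary result. Neither follows: there is no bias when no interaction exists, and the primary test and overall effect are untouched.

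**What to change.** In SAP 7.5 and 7.7.3, for subgroup analyses of the primary estimand only, replace reuse of the primary imputations with a second MAR imputation run. Run it separately by treatment arm, add the subgroup variable or variables in the form used for analysis, and keep the post-randomization NYHA and gradient terms. Imputing by arm lets each subgroup have its own treatment effect. In simulation it was essentially unbiased in every setting tried, including missingness that depends on the gradient auxiliary.

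Genotype samples come only from consenting patients (Protocol 1.3), so that variable is best added only for its own subgroup analysis. Do not substitute an observed-data analysis; keep the secondary-estimand subgroup results in SAP 7.7.4 as the observed-completer comparison.

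The cost is one extra imputation run, and subgroup estimates that come from a different imputation run than the primary result, which a table footnote can state. The primary analysis, alpha and sample size do not change.
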